#### 5.4.1 Incidence measures

The *incidence rate* (IR) measures the occurrence of new cases per unit of person-time.

$$IR = \frac{Number\ of\ new\ cases}{Total\ follow - up\ time}$$

The incidence rate takes into consideration the patient-specific follow-up time and it assumes a constant hazard rate. For each of n subjects the time  $t_k (k=1,...,K)$  to: (1) the end of the risk period, if recurrent events are allowed or (2) to the first occurrence of a certain event is observed. If the event was not experienced, the (censored) time to the end of the risk period is observed.

In the present study, women-years are conducted as a unit of person-time. Incidence rates are shown per 10^4 women-years (WY) unless otherwise specified.

The *incidence rate ratio* (IRR) is the proportion of two incidence rate estimates.

$$IRR = \frac{Incidence\ rate\ of\ treatment\ group}{Incidence\ rate\ of\ control\ group}$$

Supporting document SOP BMT 01.09 – Doc 5002.02 – Effective date 21.03.2017

The incidence rate ratio gives a measure of how much more likely an event occurs in subjects under exposure (treatment group) than in subjects who were not exposed (control group).

The *incidence proportion* (IP) measures the occurrence of new cases in relation to the size of the population at risk within a given period of time (cumulative incidence).

$$IP = \frac{Number\ of\ new\ cases}{Size\ of\ population\ at\ risk}$$

Exact 95% confidence intervals for prevalence, incidence proportion, incidence rate, and incidence rate ratio will be calculated in accordance with Clopper and Pearson[9].

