#### Risk of long-term use

- 1. Selected baseline characteristics in long-term user
- 2. Anemia (primary outcome) in long-term user
- 3. Depression (primary outcome) in long-term user
- 4. SAEs in long-term user

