#### 6.2.2 Definition of subgroups

Variable label	Definition
Country	Germany vs. Poland vs. Hungary vs. Switzerland vs. Russia vs. Ukraine
Long-term user	15 months or more of continuous EMT intake
EMT user type	Starter vs. restarter vs. switcher
Diagnosis classification	Diagnosis of endometriosis confirmed via surgery / laparoscopy vs. diagnosis based on clinical symptoms
Age categories	< 20 vs. 20 to < 30 vs. 30 to < 40 vs. >= 40
Age-standardization	Referenced population: NAED cohort

12 ICD10-Codes Version 2009

13 ATC-Codes Version 2010

14 OPS-Codes Version 2009

Supporting document SOP BMT 01.09 – Doc 5002.02 – Effective date 21.03.2017

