#### Section B-7 Distribution and selected baseline characteristics of Visanne long-term user

#### Section B-7.1 Duration of Visanne use

Table B-7.1.1 Duration of Visanne use

	DNG long-term user*
Number (%) of women	xx ( 100%)
Duration of DNG use	
15 months to < 24 months	xx ( xx.x%)
24 months to < 30 months	xx ( xx.x%)
30 months to < 36 months	xx ( xx.x%)
36 months to < 42 months	xx ( xx.x%)
42 months to < 48 months	xx ( xx.x%)
48 months to < 54 months	xx ( xx.x%)
54 months to < 60 months	xx ( xx.x%)
60 months to < 66 months	xx ( xx.x%)
66 months to < 72 months	xx ( xx.x%)
72 months to < 78 months	xx ( xx.x%)
78 months to < 84 months	xx ( xx.x%)
84 months and more	xx ( xx.x%)

Note: \*Long-term: defined as continuous use for >= 15 months. They may have started with other than DNG treatment.

Table B-7.1.2	Duration of Visanne use, Starter
Table B-7.1.3	Duration of Visanne use, Switcher
Table B-7.1.4	Duration of Visanne use, Restarter
Table B-7.1.5	Duration of Visanne use, Diagnosis confirmed by surgery
Table B-7.1.6	Duration of Visanne use, Diagnosis based on clinical symptoms
Table B-7.1.7	Duration of Visanne use, Germany
Table B-7.1.8	Duration of Visanne use, Poland
Table B-7.1.9	Duration of Visanne use, Hungary
Table B-7.1.10	Duration of Visanne use, Switzerland
Table B-7.1.11	Duration of Visanne use, Russia
Table B-7.1.12	Duration of Visanne use. Ukraine

Supporting document SOP BMT 01.09 – Doc 5002.02 – Effective date 21.03.2017

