#### INAS-VIPOS Statistical Analysis Plan V02-00

Supporting document SOP BMT 01.09 - Doc 5002.02 - Effective date 21.03.2017

Section C-2.5	Incidence rate of clinically relevant anemia for long-term use, AT population, Complete cohort
Table C-2.5.1	Incidence rate of clinically relevant anemia for long-term use, AT population, Starter
Table C-2.5.2	Incidence rate of clinically relevant anemia for long-term use, AT population, Switcher
Table C-2.5.3	Incidence rate of clinically relevant anemia for long-term use, AT population, Restarter
Table C-2.5.4	Incidence rate of clinically relevant anemia for long-term use, AT population, Diagnosis confirmed by surgery
Table C-2.5.5	Incidence rate of clinically relevant anemia for long-term use, AT population, Diagnosis based on clinical symptoms
Table C-2.5.6	Incidence rate of clinically relevant anemia for long-term use, AT population, Germany
Table C-2.5.7	Incidence rate of clinically relevant anemia for long-term use, AT population, Poland
Table C-2.5.8	Incidence rate of clinically relevant anemia for long-term use, AT population, Hungary
Table C-2.5.9	Incidence rate of clinically relevant anemia for long-term use, AT population, Switzerland
Table C-2.5.10	Incidence rate of clinically relevant anemia for long-term use, AT population, Russia
Table C-2.5.11	Incidence rate of clinically relevant anemia for long-term use, AT population, Ukraine
Section C-2.6	Incidence rate of new depression or worsening of existing depression for long-term use
Table C-2.6.1	Incidence rate of new depression or worsening of existing depression for long-term use, AT population, Complete cohort
Table C-2.6.2	Incidence rate of new depression or worsening of existing depression for long-term use, AT population, Starter
Table C-2.6.3	Incidence rate of new depression or worsening of existing depression for long-term use, AT population, Switcher
Table C-2.6.4	Incidence rate of new depression or worsening of existing depression for long-term use, AT population, Restarter
Table C-2.6.5	Incidence rate of new depression or worsening of existing depression for long-term use, AT population, Diagnosis confirmed by surgery
Table C-2.6.6	Incidence rate of new depression or worsening of existing depression for long-term use, AT population, Diagnosis based on clinical symptoms
Table C-2.6.7	Incidence rate of new depression or worsening of existing depression for long-term use, AT population, Germany

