#### Section C-3.4 Incidence rate of serious adverse events by organ system for long-term use

Table C-3.4.1 Incidence rate of serious adverse events by organ system for long-term use, AT population, Complete cohort

	DNG		OAED			NAED		Ex-use	Allocation unknown	Total
		GnRH-a	Danazol	All OAED	СНС	Other progestin	All NAED			
Number of women years*	XX	xx								
Serious adverse events**	xx	xx								
IR (95% CI) Thereof***	xx.x (xx.x-x.x)	xx.x (xx.x-x.x)	xx.x (xx.x–x.x)	xx.x (xx.x–x.x)	xx.x (xx.x-x.x)	xx.x (xx.x–x.x)	xx.x (xx.x–x.x)	xx.x (xx.x–x.x)	xx.x (xx.x-x.x)	xx.x (xx.x–x.x)
Infectious diseases	XX		XX	XX	XX		XX	XX	XX	XX
Neoplasms, malignant	xx	xx	xx.x (xx.x–x.x)	xx	XX	XX	xx.x (xx.x–x.x)	xx.x (xx.x–x.x)	xx	xx
Neoplasms, benign	xx	xx	xx.x (xx.x–x.x)	xx	xx		xx	xx.x (xx.x–x.x)	xx.x (xx.x–x.x)	xx
Diseases of the blood	xx.x (xx.x–x.x)	,	xx.x (xx.x–x.x)	xx.x (xx.x–x.x) xx	xx.x (xx.x–x.x)	xx.x (xx.x–x.x)	xx.x (xx.x–x.x)	xx.x (xx.x–x.x) xx	xx.x (xx.x–x.x) xx	xx.x (xx.x–x.x)
and blood-forming organs Endocrine diseases	xx.x (xx.x–x.x)		xx.x (xx.x–x.x)	xx.x (xx.x-x.x)	xx.x (xx.x–x.x)					
	xx.x (xx.x-x.x)	xx.x (xx.x–x.x)	xx.x (xx.x-x.x)	xx.x (xx.x-x.x)	xx.x (xx.x-x.x)					
Psychiatric and neurological disorders	xx xx.x (xx.x-x.x)	xx xx.x (xx.x–x.x)	xx xx.x (xx.x–x.x)	xx xx.x (xx.x–x.x)	xx xx.x (xx.x-x.x)		xx xx.x (xx.x–x.x)	xx xx.x (xx.x–x.x)	xx xx.x (xx.x–x.x)	xx.x (xx.x–x.x)
Eye	xx xx.x (xx.x-x.x)		xx xx.x (xx.x–x.x)	xx.x (xx.x-x.x)						
Ear	xx xx.x (xx.x–x.x)	xx.x (xx.x–x.x)								
Cardiovascular system	xx	xx	xx xx.x (xx.x–x.x)	xx	xx	, ,	xx	xx xx.x (xx.x–x.x)	xx	xx
Respiratory system	xx	xx	xx (xx.x-x.x)	xx	XX	xx	xx xx.x (xx.x-x.x)	xx xx.x (xx.x–x.x)	xx	xx

Supporting document SOP BMT 01.09 - Doc 5002.02 - Effective date 21.03.2017

Digestive system	xx			
	xx.x (xx.x-x.x)			
Skin	XX			
	xx.x (xx.x-x.x)			
Musculoskeletal system	xx			
and connective tissue	xx.x (xx.x-x.x)			
Genitourinary system	xx			
	xx.x (xx.x-x.x)			
Pregnancy, delivery and	xx			
Puerperium	xx.x (xx.x-x.x)			
Injury, poisoning,	xx			
accidents etc.	xx.x (xx.x-x.x)	xx.x (xx.x-x.x)	xx.x (xx.x–x.x)	xx.x (xx.x-x.x)

Note: \* Only women with 15 months or more of continuous EMT intake were considered. Incidence rates are calculated based on an observation time of 15 months or more

Note: \*\* Incidence rate is shown per 104 women years.

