SAEs, which occurred within 3 months after stop of EMT, were attributed to the last EMT used by the women. Therefore, pregnancy-related SAEs in XXX cohorts does not necessarily reflect unwanted pregnancies during

Note: \*\*\* Women may appear in more than one category. ICD10 Codes Version 2009.

Table C-3.4.2	Incidence rate of serious adverse events by organ system for long-term use, AT population, Starter
Table C-3.4.3	Incidence rate of serious adverse events by organ system for long-term use, AT population, Switcher
Table C-3.4.4	Incidence rate of serious adverse events by organ system for long-term use, AT population, Restarter
Table C-3.4.5	Incidence rate of serious adverse events by organ system for long-term use, AT population, Diagnosis confirmed by surgery
Table C-3.4.6	Incidence rate of serious adverse events by organ system for long-term use, AT population, Diagnosis based on clinical symptoms
Table C-3.4.7	Incidence rate of serious adverse events by organ system for long-term use, AT population, Germany
Table C-3.4.8	Incidence rate of serious adverse events by organ system for long-term use, AT population, Poland
Table C-3.4.9	Incidence rate of serious adverse events by organ system for long-term use, AT population, Hungary

- Table C-3.4.10 Incidence rate of serious adverse events by organ system for long-term use, AT population, Switzerland
- Table C-3.4.11 Incidence rate of serious adverse events by organ system for long-term use, AT population, Russia
- Table C-3.4.12 Incidence rate of serious adverse events by organ system for long-term use, AT population, Ukraine

Supporting document SOP BMT 01.09 – Doc 5002.02 – Effective date 21.03.2017

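### Long-term users are selected on completing 15 months of continuous treatment, but the SAP never starts their risk period at month 15

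*SAP*

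**What the plan says.** SAP 6.2.2 defines a long-term user by "15 months or more of continuous EMT intake". SAP 5.4.4, under Risk of long-term use, lists baseline characteristics, anemia, depression and "SAEs in long-term user" as secondary outcomes in this group.

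For the rates themselves, three places matter:

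- **SAP 5.4.1** gives the general rule: new cases divided by total follow-up time. It describes how a woman's time ends: "If the event was not experienced, the (censored) time to the end of the risk period is observed". It does not say when the risk period begins for a subgroup that is defined later than study entry.
- **Mock Table C-3.4.1** (SAEs in long-term use) has a footnote on the women-years row. Its first sentence selects the women: "Only women with 15 months or more of continuous EMT intake were considered". Its second concerns the time: "Incidence rates are calculated based on an observation time of 15 months or more". A further note says that "SAEs, which occurred within 3 months after stop of EMT, were attributed to the last EMT used by the women".
- **Mock Tables C-2.5 and C-2.6** (anemia and depression in long-term use) appear by title only, for example "Incidence rate of clinically relevant anemia for long-term use, AT population, Complete cohort". They have no shell and no note on person-time.

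The tables on dienogest (DNG) long-term users in Section B-7 add about these women: "They may have started with other than DNG treatment". The SAP does not say whether continuity means the same EMT or any EMT.

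**The concern.** Membership of the group depends on what happens during the first 15 months. A woman who dies in month 9, or whose event makes her stop for good in month 9, can never be a long-term user. If the women who do qualify then bring their first 15 months into the denominator, that time could not have contained a death or a use-ending event. This is immortal time for those events.

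Other events can occur in the early period and stay in the numerator. The resulting figure is then a blend of early and late risk, although its label presents it as the risk of long-term use.

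At stake is the interpretation of the long-term anemia, depression and SAE rates. They are the plan's only rates specific to prolonged use.

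**Working it through.** **Plan's own figure.** The documents state no long-term rate, so there is nothing to reproduce. The check compares two ways of computing the rate.

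**Inputs**

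- Threshold of 15 months: SAP 6.2.2 and the footnote to Table C-3.4.1.
- T, mean observation time in months among women who qualify: not given, so assumed. It lies between 15 and about 84, since SAP section 3 sets maximum follow-up at 7 years.
- q, share of events that end continuous use (death included): not given, so assumed from 0 to 1.
- k, hazard in the first 15 months relative to later: not given. It is taken as 1 (constant hazard) and then 2.

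**Formula.** Rate A uses the whole time of the selected women. Rate B uses events and time from month 15 on. In the first 15 months only the share 1 − q of events can be seen among women who qualify, so

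A/B = [(1 − q) × 15 × k + (T − 15)] / T.

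With k = 1 this becomes 1 − q × 15/T, so the understatement is q × 15/T. Example with q = 0.25 and T = 24: 0.25 × 15/24 = 15.6%.

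**Understatement at constant hazard (k = 1)**

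| T (months) | q = 0 | q = 0.10 | q = 0.25 | q = 0.50 | q = 1 |
|---|---|---|---|---|---|
| 24 | 0% | 6.2% | 15.6% | 31.2% | 62.5% |
| 36 | 0% | 4.2% | 10.4% | 20.8% | 41.7% |
| 60 | 0% | 2.5% | 6.2% | 12.5% | 25.0% |
| 84 | 0% | 1.8% | 4.5% | 8.9% | 17.9% |

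The q = 1 column is the ceiling for a given T. It applies to deaths and to events that always end use. A T closer to 15 raises every entry except those at q = 0.

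**Early hazard twice the late one (k = 2).** At q = 0, A/B is 1.62 for T = 24, 1.42 for T = 36 and 1.18 for T = 84. At q = 0.25 it is 1.31, 1.21 and 1.09. The direction turns where (1 − q) × k = 1. At q = 0.25 that is k = 1/0.75 = 1.33; above it, rate A is too high.

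**Simulation check.** Assumptions: 500 events per 10,000 women-years, a stopping rate of 0.30 per year, and a cap of 84 months. Mean T came out at 44.7 to 47.8 months. A/B was 1.00, 0.97, 0.92, 0.84 and 0.66 for q = 0, 0.10, 0.25, 0.50 and 1, in line with the formula. Rate B returned 497 to 502 per 10,000 women-years for every q, against 500 assumed.

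**The case against.** The strongest reply is that the footnote may already mean what it should. Its first sentence restricts the table to women with at least 15 months of use. A second sentence saying only that their time is at least 15 months would add almost nothing. Read as time from month 15 on, it has a function of its own and there is no bias. This stands as a possible reading, but the text does not choose it, and the general rule in SAP 5.4.1 points to whole time.

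Several stronger conclusions are tempting, and the documents do not support them:

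- **That the first 15 months are free of events.** Table C-3.4.1 counts infections, benign neoplasms, skin disease, injuries and much else. Such events need not end treatment. If continuity means any EMT, even a woman who switches after an event without a break may still qualify. Only the share q is removed.
- **That the rate is understated by 42% to 62%.** Those are the q = 1 values for T of 36 and 24 months.
- **That prolonged use is made to look safer.** A higher early hazard reverses the direction. The protocol introduction reports that bleeding symptoms on dienogest tended to lessen late in a 52-week study, which hints at this for anemia.
- **That the bias differs by drug because few users of the other approved treatments reach 15 months.** The formula depends on q and T among women who qualify, not on how many qualify. Neither is given by drug.
- **That the footnote governs anemia and depression.** It stands on the SAE table only. For C-2.5 and C-2.6 the person-time is simply unspecified.
- **That a general long-term objective is at risk.** The secondary objective on short- and long-term use concerns adolescents. Long-term use in general is a secondary outcome in SAP 5.4.4, and C-3.4 belongs to the other safety outcomes.

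**Conclusion.** The gap is real and limited. Selection depends on reaching month 15, and nothing in the SAP starts women-years or events there. The default rule of total follow-up time would therefore count a period in which deaths and use-ending events could not appear. If the footnote is applied as time from month 15, there is no dilution. If whole time is counted and the hazard is constant, the understatement is q × 15/T. Events that rarely stop treatment are little affected; deaths and events that always end use are affected most. A higher early hazard can turn the understatement into an overstatement. Because q, T and the shape of the hazard are all assumptions, neither size nor sign can be fixed from the documents.

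The affected tables are descriptive. Section D inference and the primary hazard ratios do not depend on them. The change is still worth making, because it removes the problem under either reading.

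**What to change.** In Tables C-2.5, C-2.6 and C-3.4, use delayed entry. A woman enters at month 15 of a continuous episode, and only women-years and events from that date count, in the cohort in use at the time. Put the rule in SAP 6.2.2 or 5.4.1 so that it covers all three tables, and reword the footnote to Table C-3.4.1 to match.

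State also whether continuity means the same EMT or any EMT, since DNG long-term users may have begun on another treatment. For SAEs attributed up to 3 months after stopping, say that they count here only if the woman had already reached month 15.

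The cost is a few sentences, a changed entry date and fewer women-years. Each qualifying woman gives up 15 months, a fraction 15/T of the whole-time total: 62.5% at T = 24, 41.7% at T = 36 and 17.9% at T = 84. Confidence intervals in these tables widen accordingly. Earlier events are not lost, because they stay in the overall Tables C-1.1, C-1.2 and C-3.3.

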#### Section C-3.5 Incidence rate of malignant neoplasms by organ system

Table C-3.5.1 Incidence rate of malignant neoplasms by organ system, AT population, Complete cohort

	DNG		OAED			NAED		Ex-use	Allocation unknown	Total
		GnRH-a	Danazol	All OAED	СНС	Other progestin	All NAED			
Number of women years	xx	xx	xx	xx	xx	xx	xx	xx	xx	xx
Malignant neoplasms	xx	xx	xx	xx	xx	xx	xx	xx	xx	xx
IR* (95% CI)	xx.x (xx.x–x.x)	xx.x (xx.x-x.x)	xx.x (xx.x-x.x)	xx.x (xx.x-x.x)	xx.x (xx.x–x.x)	xx.x (xx.x-x.x)	xx.x (xx.x-x.x)	xx.x (xx.x-x.x)	xx.x (xx.x-x.x)	xx.x (xx.x–x.x)
Breast	xx	xx	xx	xx	xx	xx	xx	xx	xx	xx
	xx.x (xx.x-x.x)	xx.x (xx.x-x.x)	xx.x (xx.x-x.x)	xx.x (xx.x-x.x)	xx.x (xx.x-x.x)					
Cervix uteri	XX	xx	xx	XX	XX	xx	XX	xx	xx	XX
	xx.x (xx.x-x.x)	xx.x (xx.x-x.x)	xx.x (xx.x-x.x)	xx.x (xx.x-x.x)	xx.x (xx.x-x.x)					
Corpus uteri and uterus	xx	xx	xx	xx	XX	xx	XX	xx	xx	xx
unspecified	xx.x (xx.x-x.x)	xx.x (xx.x-x.x)	xx.x (xx.x-x.x)	xx.x (xx.x-x.x)	xx.x (xx.x-x.x)					
Ovary	xx	xx	xx	xx	XX	xx	xx	XX	xx	xx
	xx.x (xx.x-x.x)	xx.x (xx.x-x.x)	xx.x (xx.x-x.x)	xx.x (xx.x-x.x)	xx.x (xx.x-x.x)					
Fallopian tube	XX	XX	XX	XX	XX	XX	XX	xx	XX	XX
	xx.x (xx.x–x.x)	xx.x (xx.x–x.x)	xx.x (xx.x-x.x)	xx.x (xx.x–x.x)	xx.x (xx.x–x.x)	xx.x (xx.x-x.x)	xx.x (xx.x–x.x)	xx.x (xx.x–x.x)	xx.x (xx.x-x.x)	xx.x (xx.x–x.x)
Vagina	XX	XX	xx	XX	XX	xx	XX	xx	xx	XX
	xx.x (xx.x–x.x)	xx.x (xx.x–x.x)	xx.x (xx.x-x.x)	xx.x (xx.x–x.x)	xx.x (xx.x–x.x)	xx.x (xx.x-x.x)	xx.x (xx.x–x.x)	xx.x (xx.x–x.x)	xx.x (xx.x-x.x)	xx.x (xx.x–x.x)
Vulva	XX	XX	XX	XX	XX		XX	XX	XX	XX
	xx.x (xx.x–x.x)	xx.x (xx.x–x.x)	xx.x (xx.x-x.x)	xx.x (xx.x-x.x)	xx.x (xx.x–x.x)					
Unspecified genital	XX	XX	XX	XX	XX	XX	XX	XX	XX	XX
	xx.x (xx.x-x.x)	xx.x (xx.x-x.x)	xx.x (xx.x–x.x)	xx.x (xx.x–x.x)	xx.x (xx.x–x.x)	xx.x (xx.x–x.x)	xx.x (xx.x–x.x)	xx.x (xx.x-x.x)	xx.x (xx.x–x.x)	xx.x (xx.x–x.x)
Placenta	XX		XX	XX	XX	XX	XX	XX	XX	XX
	xx.x (xx.x-x.x)	xx.x (xx.x-x.x)	xx.x (xx.x–x.x)	xx.x (xx.x–x.x)	xx.x (xx.x–x.x)	xx.x (xx.x–x.x)	xx.x (xx.x–x.x)	xx.x (xx.x-x.x)	xx.x (xx.x–x.x)	xx.x (xx.x–x.x)
Subtotal of gyn. cancer	хх	XX	XX	XX	XX	XX	хх	XX	XX	XX

Supporting document SOP BMT 01.09 – Doc 5002.02 – Effective date 21.03.2017

	xx.x (xx.x–x.x)	xx.x (xx.x–x.x)	xx.x (xx.x-x.x)	xx.x (xx.x-x.x)	хх.х (хх.х–х.х)	xx.x (xx.x–x.x)	xx.x (xx.x-x.x)	хх.х (хх.х– х.х)	xx.x (xx.x– x.x)	xx.x (xx.x-x.x)
Lip, oral cavity and	xx	XX	xx							
pharynx	xx.x (xx.x-x.x)	xx.x (xx.x-x.x)	xx.x (xx.x-x.x)							
Digestive organs	xx	xx	xx							
	xx.x (xx.x-x.x)	xx.x (xx.x-x.x)	xx.x (xx.x-x.x)							
Respiratory and	xx	xx	xx							
intrathoracic organs	xx.x (xx.x-x.x)	xx.x (xx.x-x.x)	xx.x (xx.x-x.x)	xx.x (xx.x-x.x)	xx.x (xx.x–x.x)	xx.x (xx.x-x.x)	xx.x (xx.x-x.x)	xx.x (xx.x-x.x)	xx.x (xx.x-x.x)	xx.x (xx.x-x.x)
Bone and articular	XX	xx	xx							
cartilage organs	xx.x (xx.x-x.x)	xx.x (xx.x-x.x)	xx.x (xx.x-x.x)	xx.x (xx.x-x.x)	xx.x (xx.x–x.x)	xx.x (xx.x-x.x)	xx.x (xx.x-x.x)	xx.x (xx.x-x.x)	xx.x (xx.x-x.x)	xx.x (xx.x-x.x)
Skin	XX	XX	xx							
	xx.x (xx.x–x.x)	xx.x (xx.x-x.x)	xx.x (xx.x–x.x)	xx.x (xx.x–x.x)	xx.x (xx.x–x.x)	xx.x (xx.x-x.x)	xx.x (xx.x–x.x)	xx.x (xx.x-x.x)	xx.x (xx.x–x.x)	xx.x (xx.x–x.x)
Mesothelial and	XX	XX	XX							
soft tissue	xx.x (xx.x–x.x)	xx.x (xx.x–x.x)	xx.x (xx.x-x.x)	xx.x (xx.x-x.x)	xx.x (xx.x–x.x)	xx.x (xx.x-x.x)	xx.x (xx.x-x.x)	xx.x (xx.x-x.x)	xx.x (xx.x-x.x)	xx.x (xx.x–x.x)
Urinary tract	XX	XX	xx							
	xx.x (xx.x–x.x)	xx.x (xx.x–x.x)	xx.x (xx.x-x.x)	xx.x (xx.x-x.x)	xx.x (xx.x–x.x)	xx.x (xx.x-x.x)	xx.x (xx.x-x.x)	xx.x (xx.x-x.x)	xx.x (xx.x-x.x)	xx.x (xx.x–x.x)
Eye, brain and other	XX	XX	XX							
parts of central nervous system	xx.x (xx.x–x.x)	xx.x (xx.x–x.x)	xx.x (xx.x–x.x)							
Thyroid and other	XX	xx	xx							
endocrine glands	xx.x (xx.x-x.x)	xx.x (xx.x-x.x)	xx.x (xx.x-x.x)							
III-defined, secondary	xx	xx	xx							
and unspecified sites	xx.x (xx.x-x.x)	xx.x (xx.x-x.x)	xx.x (xx.x-x.x)							
Lymphoid,	xx	xx	xx							
hematopoietic and related tissue	xx.x (xx.x-x.x)	xx.x (xx.x–x.x)	xx.x (xx.x–x.x)	xx.x (xx.x-x.x)						
Subtotal of none	хх	хх	хх	хх	хх	xx	хх	xx	хх	хх
gyn. cancer	xx.x (xx.x–x.x)	xx.x (xx.x-x.x)	xx.x (xx.x-x.x)	xx.x (xx.x–x.x)	xx.x (xx.x–x.x)	xx.x (xx.x-x.x)	xx.x (xx.x-x.x)	xx.x (xx.x– x.x)	xx.x (xx.x– x.x)	xx.x (xx.x-x.x)

Note: \* Incidence rate is shown per 10^4 women years.

Table C-3.5.2	Incidence rate of malignant neoplasms by organ system, AT population, Starter
Table C-3.5.3	Incidence rate of malignant neoplasms by organ system, AT population, Switcher
Table C-3.5.4	Incidence rate of malignant neoplasms by organ system, AT population, Restarter
Table C-3.5.5	Incidence rate of malignant neoplasms by organ system, AT population, Diagnosis confirmed by surgery
Table C-3.5.6	Incidence rate of malignant neoplasms by organ system, AT population, Diagnosis based on clinical symptoms
Table C-3.5.7	Incidence rate of malignant neoplasms by organ system, AT population, Germany
Table C-3.5.8	Incidence rate of malignant neoplasms by organ system, AT population, Poland
Table C-3.5.9	Incidence rate of malignant neoplasms by organ system, AT population, Hungary
Table C-3.5.10	Incidence rate of malignant neoplasms by organ system, AT population, Switzerland
Table C-3.5.11	Incidence rate of malignant neoplasms by organ system, AT population, Russia
Table C-3.5.12	Incidence rate of malignant neoplasms by organ system, AT population, Ukraine

Supporting document SOP BMT 01.09 - Doc 5002.02 - Effective date 21.03.2017

